- Change from baseline in overall clinical SD score at 4 weeks of treatment with ruxolitinib 1.5% cream applied twice daily

- Change from baseline in each component of the clinical SD score at 4 weeks of treatment with ruxolitinib 1.5% cream applied twice daily (scale, erythema, pruritus)
- Change in overall clinical SD at 6 weeks (i.e., 2 weeks after treatment cessation) from baseline and from 4 weeks
- The frequency, duration, and severity of AEs
- Changes in vital signs
- Changes in laboratory data for hematology, serum chemistry, and urinalysis

Mechanistic (Exploratory) Endpoints

- Determine the molecular cutaneous phenotype of SD at baseline compared with healthy controls, using transcriptomic and proteomic approaches from skin samples acquired by tape-strips
- Identify molecular markers that correlate with disease activity in SD at baseline
- Characterize the change in molecular responses with treatment of topical ruxolitinib 1.5% cream after 4 weeks of treatment
- Identify molecular markers that correlate with treatment response at 4 weeks

STUDY DESIGN OVERVIEW:

This study is an open-label prospective interventional trial. The study will take place at Icahn School of Medicine at Mount Sinai.

The study will include 25 adult patients with moderate-to-severe-SD as well as 20 age- and gender-matched healthy control subjects for comparison. The SD patients will have baseline clinical score of at least 6 using the SD Severity Score in Appendix 1, or an Investigator Global Assessment (IGA) score of at least 3. Enrolled SD subjects will apply topical ruxolitinib 1.5% cream twice daily for 4 weeks. They will return for visits at weeks 2, 4, and 6 following study treatment initiation for repeat clinical assessments, medication reviews, tape-strip, blood and urine sample collections, and monitoring for adverse events.

After providing consent, all subjects will be assessed for study eligibility, which includes a review of the subjects past and current medical conditions, familial medical history and detailed review of past and current medications. SD subjects will also undergo a review of past topical treatments/therapies for SD, and clinical assessments (clinical SD score and IGA).

Subjects who meet inclusion criteria for eligibility may continue with the Baseline Visit (Week 0) or can be scheduled to return for the Baseline Visit within 28 days of the Screening Visit.

SD Subjects:

Seborrheic Dermatitis Ruxolitinib Cream Protocol
Incyte IIR

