- Review personal and family history of SD and other inflammatory skin diseases
- Record all concomitant medications as well as all those received within 30 days prior to screening
- Record all prior therapies for SD
- Urine pregnancy test for all female subjects of child-bearing potential
- SD Clinical assessments (IGA, SD Severity Score)
- Record adverse events

* If subject meets all entry criteria at Screening, he/she can complete Baseline Visit on the same day (identical procedures do not need to be repeated). If more than 28 days has lapsed between screening and Baseline/Visit 2, then all procedures should be repeated except for re-obtaining informed consent. If subject has used a topical medication, then Baseline/Visit 2 will occur only after a 1 week washout period.

Visit 2 – Baseline (Week 0)

- Confirm all inclusion and exclusion criteria have been met
- Record concomitant medications and adverse events
- DLQI questionnaire
- Standardized clinical photography (including photographs of subject's entire face and close up photographs of the following facial regions: 1. Left cheek, 2. Right cheek, 3. Forehead and glabella)
- SD clinical assessments (IGA, SD Severity Score)
- Urine pregnancy test for all female subjects of child-bearing potential

- Collect blood samples for CBC with differential, Comprehensive metabolic panel (CMP), and C-reactive protein (CRP)
- Collect blood sample for possible future mechanistic analyses
- Urinalysis
- Perform tape strips of lesional and non-lesional skin. Lesional skin tape strips will be taken from area of worst clinical involvement
- Dispense/administer study drug

Visit 3 – Week 2

- Record concomitant medications and adverse events
- DLQI questionnaire
- SD clinical assessments (IGA, SD Severity Score)
- Urine pregnancy test for all female subjects of child-bearing potential
- Perform tape strips of lesional skin. Lesional skin tape strips will be taken from the same location as the lesional tape strips taken at Baseline.
- Dispense study drug and assess compliance. Subjects will report each study drug application, with 4 missed doses from Baseline considered non-compliance.

Visit 4 – Week 4

- Record concomitant medications and adverse events
- DLQI questionnaire
- Standardized clinical photography (including photographs of subject's entire face and close up photographs of the following facial regions: 1. Left cheek, 2. Right cheek, 3. Forehead and glabella)

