- SD clinical assessments (IGA, SD Severity Score)
- Urine pregnancy test for all female subjects of child-bearing potential
- Collect blood samples for CBC with differential, Comprehensive metabolic panel (CMP), and C-reactive protein (CRP)
- Collect blood sample for possible future mechanistic analyses
- Urinalysis
- Perform tape strips of lesional skin. Lesional skin tape strips will be taken from the same location as the lesional tape strips taken at Baseline and Week 2.
- Assess study drug dosing compliance and retrieve all remaining study drug from subject. Subjects will report each study drug application, with 4 missed doses from Week 2 considered non-compliance.

Visit 5 – Week 6

- Record concomitant medications and adverse events
- DLQI questionnaire

- Standardized clinical photography including photographs of subject's entire face and close up photographs of the following facial regions: 1. Left cheek, 2. Right cheek, 3. Forehead and glabella)
- SD clinical assessments (IGA, SD Severity Score)
- Urine pregnancy test for all female subjects of child-bearing potential
- Perform tape strips of lesional skin. Lesional skin tape strips will be taken from the same location as the lesional tape strips taken at Baseline, Week 2, and Week 4.

Early Termination Visit (if applicable)

- Record concomitant medications and adverse events
- DLQI questionnaire
- Standardized clinical photography (including photographs of subject's entire face and close up photographs of the following facial regions: 1. Left cheek, 2. Right cheek, 3. Forehead and glabella)
- Urine pregnancy test for all female subjects of child-bearing potential
- Collect blood samples for CBC with differential, Comprehensive metabolic panel (CMP), and C-reactive protein (CRP)
- Collect blood sample for possible future mechanistic analyses
- Urinalysis
- SD clinical assessments (IGA, SD Severity Score)
- Perform tape strips of lesional skin. Lesional skin tape strips will be taken from the same location as the lesional tape strips taken at Baseline and Week 2 (if applicable)
- Assess study drug dosing compliance and retrieve all remaining study drug from subject

For Control Subjects

Visit 1 – Screening (within 28 days of Baseline)*

- Obtain signed IRB-approved informed consent and HIPPA agreement
- Review Inclusion and Exclusion Criteria
- Record gender, race, ethnicity, and medical history
- Review personal and family medical conditions/diseases

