The reasons why a subject may discontinue or be withdrawn from the study by the investigator include, but are not limited to the following: subject request, protocol violation, loss to follow up, subject non-compliance, defined as 4 missed applications during the 2 week period between study Visits, study termination by investigators, and a confirmed grade 3 or higher adverse event, which is suspected to be related to study drug administration. Subjects that elect to withdraw from the trial due to lack of efficacy and/or exacerbation of disease will undergo the following: vital signs; blood test; pregnancy test (if applicable); clinical photography; SD clinical assessments; DLQI questionnaire, assessment of concomitant medication and adverse events; blood collection for future mechanistic analysis; lesional tape strip collection.

Stopping Rules

Patients will be permanently discontinued from study treatment in the event of:

- Anaphylactic reaction or other severe systemic reaction to study drug application
- Pregnancy at anytime during the study period
- Diagnosis of a malignancy during study, excluding carcinoma in situ of the cervix, or squamous or basal cell carcinoma of the skin
- Any infection that is opportunistic, whose nature or course may suggest an immuno-compromised status
- Treatment with any prohibited concomitant medication or procedure
- Other reasons that may lead to the permanent discontinuation of study drug include certain Aes deemed related to the study drug.
- If the following lab results are abnormal, participants will be retested in a window of 7-10 days and reassessed. If the test results remain abnormal, participants will be discontinued from the study:

Hematology

Absolute Neutrophil Count: $<1000/\text{mm}^3$; $<1.0 \times 10^9/\text{L}$

Hemoglobin: $<8.0 \text{ g/dL}$; $<4.96 \text{ mmol/L}$; $<80 \text{ g/L}$

Hemoglobin drop $\geq 2 \text{ g/dL}$ from baseline on two consecutive blood draws with associated symptoms; or hemoglobin drop $\geq 3 \text{ g/dL}$ from baseline on two consecutive blood draws without associated symptoms.

Platelet count: $<75,000/\text{mm}^3$; $<75.0 \times 10^9/\text{L}$

Lymphocytes: $<500/\text{mm}^3$; $<0.5 \times 10^9/\text{L}$

Chemistry

AST $>3.0 \times \text{ULN}$

ALT $>3.0 \times \text{ULN}$

Total bilirubin $>1.5 \times \text{ULN}$

CPK $>10 \times \text{ULN}$

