An "Initial Pregnancy Report" or equivalent must be completed in full and emailed to [contact] or faxed to [name] within 24 hours of discovery of a pregnancy of a subject who has taken the Incyte product or the pregnancy of a partner for a subject who has taken the Incyte product. The "Follow-up Pregnancy Report Form" or equivalent must be completed and emailed to [contact] or faxed to [name] within 30 days after delivery, so that Incyte is provided with information regarding the outcome of the pregnancy. If the pregnancy results in any events which meet the serious criteria (i.e., miscarriage or termination), the SAE reporting process needs to be followed and the timelines associated with a SAE should be followed.

SUBJECT IDENTIFICATION

Subjects are numbered sequentially. Each subject will be assigned a unique screening number for the duration of the study. Subject screening numbers will not be reassigned or reused for any reason. The investigator must maintain a master log linking the subject number to the subject's name. The investigator must follow all applicable privacy laws in order to protect a subject's privacy and confidentiality.

STUDY DRUG SUPPLY:

Seborrheic Dermatitis Ruxolitinib Cream Protocol
Incyte IIR
March 25, 2022

Eligible patients will receive a supply of ruxolitinib 1.5% cream which they will apply to affected skin on the face only twice daily. Patients will be instructed not to use more than 60g of cream per week.

All study medication will be stored in a secure cool area between 15-30°C. Study drug will be provided to subjects at each study visit, with initial application performed at that time and subsequent applications performed by the patients at home.

Subjects will be queried during each study visit on any missed applications.

STATISTICAL CONSIDERATIONS:

Sample Size Calculation

A sample size of n=20 SD patients guarantees 90% power at 2.1% significance to detect a minimum proportion of 75% of patients with IGA 0/1 at week 4. This calculation assumes the application of the one-sided binomial test with a null hypothesis proportion of 40%. This proportion is based on the vehicle response benchmark reported by Zirwas et al.(2021) when comparing IGA 0/1 at week 8 in 154 patients treated with roflumilast foam 0.3% vs. 72 patients in the vehicle-controlled group(18). Accounting for a 20% dropout rate, we, therefore, propose a sample size of n=25 patients.

Mechanistic Endpoint

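### Four self-reported missed applications in two weeks can take a patient out of the study, not just off the cream, and so lose the Week 4 primary IGA or the Week 6 score

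*Combined protocol and SAP*

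**What the plan says.** Under Discontinuation of Treatment and Withdrawal of Subjects, the protocol opens its list with "The reasons why a subject may discontinue or be withdrawn from the study by the investigator include, but are not limited to the following". One listed reason is "subject non-compliance, defined as 4 missed applications during the 2 week period between study Visits".

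The count is taken at two visits and rests on the patient's own report:

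- Visit 3 (Week 2): "Subjects will report each study drug application, with 4 missed doses from Baseline considered non-compliance".
- Visit 4 (Week 4): "Subjects will report each study drug application, with 4 missed doses from Week 2 considered non-compliance". At this visit the IGA and SD Severity Score are also recorded and the remaining cream is collected.

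The Stopping Rules that follow are a separate, mandatory list, introduced by "Patients will be permanently discontinued from study treatment in the event of". Missed applications are not on it.

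The primary endpoint is the proportion with IGA 0/1 at Week 4. A secondary endpoint uses the Week 6 score: "Change in overall clinical SD at 6 weeks (i.e., 2 weeks after treatment cessation) from baseline and from 4 weeks". The Early Termination visit includes an IGA, but no text says it replaces the Week 4 value, and no text asks a withdrawn patient to come back at Week 4 or Week 6. Analysis of Primary Endpoint names the one-sided binomial test against 0.4 without an analysis set or a rule for missing values. On sample size, the protocol says "Accounting for a 20% dropout rate, we, therefore, propose a sample size of n=25 patients".

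**The concern.** Stopping a cream and leaving a study are different events, and the protocol attaches non-adherence to the second. The consequences depend on when the rule is met.

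- **At Week 2.** Withdrawal can remove the Week 4 primary IGA and the Week 6 score. An Early Termination IGA would be taken around Week 2, so it is not a Week 4 outcome.
- **At Week 4.** The four weeks of treatment are complete and the primary IGA is due at that visit. Withdrawal cannot change exposure. Among the efficacy scores it can only lose Week 6. The Week 6 DLQI, photographs, tape strips and adverse event record would go with it.

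Missed applications may well be related to poor response or poor tolerability. The trial is open-label with one treated arm, its primary result is a single proportion, and the Week 2 IGA is scored at the visit where the rule is first checked. The investigator deciding on withdrawal may therefore already know how the patient is doing. The data lost this way would be avoidable and possibly related to outcome. The safety protections do not depend on this ground: the Stopping Rules and the ground for related grade 3 or higher adverse events both stand without it.

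**Working it through.** **Inputs from the protocol.** Twice-daily application, so 2 × 14 = 28 applications per two-week interval and 56 in total; threshold of 4 missed; null proportion 0.40, alternative 0.75, one-sided exact binomial test; 20 evaluable and 25 enrolled patients.

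**Threshold.** 4/28 = 14.3% missed, and 24/28 = 85.7% adherence in the interval.

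**The plan's own figures reproduce.** With success at 13 or more of 20:

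- P(X ≥ 13 | 20, 0.40) = 0.0210 (stated 2.1%).
- P(X ≥ 13 | 20, 0.75) = 0.898 (stated 90%).
- 20/(1 − 0.20) = 25, so the dropout allowance is 5 of 25.

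**How many patients could meet the rule.** The documents give no miss rate, so a per-application miss probability p is assumed, with independent misses and 4 missed read as at least 4. The chance of meeting the rule in one interval is q = P(X ≥ 4), X ~ Bin(28, p). Only Week 2 flags can lose the primary IGA.

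| p | q | Expected Week 2 flags, 25q | Chance that more than 5 of 25 are flagged | First flagged at Week 4, 25q(1 − q) |
|---|---|---|---|---|
| 5% | 0.0491 | 1.23 | 0.001 | 1.17 |
| 8% | 0.1820 | 4.55 | 0.297 | 3.72 |
| 10% | 0.3054 | 7.64 | 0.822 | 5.30 |

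These are flags, not withdrawals. They equal withdrawals only if the investigator acts every time. At 2% and 3% missed, the expected Week 2 flags are 0.06 and 0.23. Clustered misses would change all of these counts.

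**Effect on the primary result if withdrawn patients are left out.** Suppose five are withdrawn at Week 2 and only patients with a Week 4 IGA are analysed. Take 13 responders among the remaining 20, and compare with the result had the five been kept (one-sided exact test against 0.40):

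| Responders among the five | Result with all 25 | p |
|---|---|---|
| Not analysed | 13/20 (65%) | 0.021 |
| 0 | 13/25 (52%) | 0.154 |
| 2 | 15/25 (60%) | 0.034 |
| 3 | 16/25 (64%) | 0.013 |

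**False-positive chance in a worst case.** Let the overall rate be 10/25 = 40%, let all m withdrawn patients be non-responders, and drop them. The retained rate is 10/(25 − m). Using Bin(25 − m, 10/(25 − m)) and the smallest cut-off with nominal level no greater than that of the planned 13/20 rule (0.0210):

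- m = 0, need 16/25: 0.013
- m = 2, need 15/23: 0.030
- m = 4, need 14/21: 0.063
- m = 5, need 13/20: 0.132

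**Power if withdrawn patients are counted as failures.** With 25 in the denominator, success needs 16 or more. With a true rate of 75% among the rest, power is P(X ≥ 16 | 25 − m, 0.75): 0.929 for m = 0, 0.804 for m = 2, 0.567 for m = 4 and 0.415 for m = 5.

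**The case against.** **The rule is optional.** The text says a subject may be withdrawn, and the visit instructions only label four missed doses as non-compliance. This stands, and it makes the flag counts upper bounds. It does not remove the problem, because discretion is what allows selective removal.

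**The harm comes from the missing analysis rule.** Whether the proportion is biased up or down depends on how missing Week 4 values are handled, which the plan does not say. This is correct about direction and size. But both simple treatments can do damage, one through possible selection and the other through lost power, and keeping the patients avoids both.

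**The numbers are assumed.** At 5% missed, the allowance of five is almost never exceeded; it is typically exceeded only near 10%. The 13/20 example needs exactly five withdrawals with at most two responders among them. If the five respond like the others (about 3 of 5), the conclusion survives at p=0.013. The p=0.034 case fails only against the 2.1% level used for sample size; the analysis section states no level. All of this stands.

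**The direction is not known.** Patients who clear early may also skip applications, and removing them would lower the proportion. This is possible, but it is equally a reason to keep them.

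**The protocol uses its terms loosely.** The persistent laboratory abnormality rule, inside the Stopping Rules, also speaks of discontinuation from the study, and other withdrawal grounds lose Week 4 in the same way. This is true, but it does not cure the non-compliance ground.

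**It is a choice of estimand.** The endpoint concerns cream applied twice daily, so an interest in adherent patients is defensible. A supportive table by adherence serves that interest without discarding outcomes.

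**Conclusion.** The concern holds. The protocol allows withdrawal from the study at 85.7% adherence in an interval and has no provision for keeping the patient's later assessments. The Week 2 limb matters most, because it can remove the primary outcome. The Week 4 limb is minor: it serves no treatment purpose and risks Week 6 data.

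The size is uncertain. Two to five Week 2 withdrawals, all within the dropout allowance, are enough to matter: a worst-case false-positive chance of 0.030 to 0.132 if non-responders are dropped, or power of 0.804 to 0.415 if the patients are counted as failures. These figures rest on assumed withdrawal numbers and assumed handling of missing values. The link between missed applications and outcome is plausible, but the documents do not establish it. The stated sample size is not in dispute. This is a change that should be made, not a fatal flaw.

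**What to change.** In Discontinuation of Treatment and Withdrawal of Subjects:

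1. Separate stopping the cream from leaving the study.
2. State that missed applications are not a reason for withdrawal from the study, including when classed as a protocol violation or brought in through the open-ended wording of the list.
3. Record missed applications as a deviation at Visits 3 and 4.
4. Unless the patient withdraws consent, keep the scheduled Week 4 and Week 6 assessments. Count the Week 4 IGA in the primary proportion and the Week 6 score in the secondary analysis.
5. Add a supportive table of Week 4 response by total missed applications out of 56.

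The cost is protocol wording. Both visits are already scheduled and the safety stopping rules do not change. The downside is that the response rate will include less adherent patients and may be slightly lower. If all 25 patients have a Week 4 IGA, the cut-off of 16/25 gives a one-sided level of 0.0132 and power of 0.929 at a true rate of 75%, assuming response does not depend on adherence.

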Safety will be evaluated by tabulations of adverse events (AEs) and will be presented with descriptive statistics at each visit. AEs will be coded using the CTCAE, Common Terminology Criteria for Adverse Events, V 5.0. The number and percentage of subjects/lesions experiencing an AE/SAE will be stratified by system organ class, or a preferred term, and/or severity of the adverse event, and recorded and tabulated overall by each sub-strata. Each subject will be counted only once within a system organ class or a preferred term using the adverse events with the highest severity within each category. All information pertaining to adverse events noted during the study will be listed by subject, detailing verbatim given by the investigator, preferred term, system organ class, date of onset, date of resolution, severity, and relationship to treatment. A tabulation of AEs will be provided by subject.

DLQI (Dermatology Life Quality Index)

The DLQI is a validated questionnaire consisting of 10 questions that has been used in many randomized controlled trials in dermatology (20, 21).

Scoring

The scoring of each question is as follows:

Very much	scored 3
A lot	scored 2
A little	scored 1
Not at all	scored 0
Not relevant	scored 0

Question unanswered	scored 0
---------------------	----------

The DLQI is calculated by summing the score of each question. The maximum score is 30 and minimum score is 0. Higher score represents a quality of life that is more impaired.

Definition of DLQI Scores

0-1 = no effect at all on patient's life

2-5 = small effect on patient's life

6-10 = moderate effect on patient's life

11-20 = very large effect on patient's life

21-30 = extremely large effect on patient's life

A change in DLQI score of at least 4 points is considered clinically important (22). Such change suggests that there has actually been a meaningful change in that patient's quality of life since the previous measurement of his/her DLQI scores.

Table 1. Schedule of Events

Visit Week	(Up to -28 Days before Baseline)	0	2	4	6	X	Control Subjects
Visit #	1	2	3	4	5	Early Termination	1
Visit Type	Screening	Baseline	Tx	Tx	F-up		Screening / Baseline
Informed Consent	X						X
Inclusion / Exclusion Criteria	X	X ³					X
Demographics and Medical Hx¹	X						X
Urine Pregnancy Test	X	X ³	X	X	X	X	X
CBC w/differential; CMP; Urinalysis		X		X		X	X
Blood Sample Stored for Future Analysis		X		X		X	X
CRP		X		X			X
SD Clinical Assessments (IGA, SD Severity Score)	X	X ³	X	X	X	X	

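### From scheduled blood tests, the laboratory stopping limits cannot stop dosing for an abnormality that arises on treatment, and no visit names a CPK test

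*Combined protocol and SAP*

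**What the plan says.** The Stopping Rules open with "Patients will be permanently discontinued from study treatment in the event of", followed by a list. One item covers hematology limits (neutrophils, hemoglobin, hemoglobin drop, platelets, lymphocytes) and chemistry limits (AST, ALT, total bilirubin, CPK above 10 times the upper limit of normal). It works in two steps. First: "If the following lab results are abnormal, participants will be retested in a window of 7-10 days and reassessed". Then: "If the test results remain abnormal, participants will be discontinued from the study".

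The Table 1 row "CBC w/differential; CMP; Urinalysis" is marked, for SD subjects, at Week 0, Week 4 and Early Termination only. The visit lists under Procedures agree. The Week 2 list contains no blood draw, and its drug item reads "Dispense study drug and assess compliance". The Week 4 list draws CBC, CMP and CRP and also contains "Assess study drug dosing compliance and retrieve all remaining study drug from subject". The Early Termination list likewise takes back the drug. Week 6 has no CBC or CMP.

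Appendix 5 records the laboratory limits as an addition under Amendment 1. Its itemized changes include none to the visit lists or Table 1.

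**The concern.** A rule meant to end treatment needs a result that arrives while treatment can still be ended. Here the first scheduled result after dosing begins comes at the visit where dosing ends, and the confirming result comes later still. A patient with a silent low count or raised AST or ALT at Week 2 would be given more drug and could complete all 4 weeks unless someone chose to test.

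Two further points follow. Once dosing is over, the item's literal action takes the patient out of the study just when follow-up of a confirmed abnormality matters most. And a limit on an analyte that no visit names may have no data behind it at all.

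**Working it through.** The plan states no figure to reproduce on this point. The check is calendar arithmetic plus a comparison of the limits with the listed tests.

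**Inputs.** Dosing is twice daily for 4 weeks (Study Design Overview), taken as day 0 to day 28. Weeks 2, 4 and 6 are taken as days 14, 28 and 42. The retest comes 7 to 10 days after the abnormal result (Stopping Rules), counted here from the draw. Draw dates are from the visit lists and Table 1.

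**1. Scheduled draws on treatment.** CBC/CMP draws after day 0 and before day 28: 0.

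**2. Confirmation dates.** Retest = draw day + 7 to draw day + 10. Dosing days left = 28 minus retest day, or 0 if that is negative.

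| First abnormal draw | Retest | Dosing days left |
|---|---|---|
| Baseline, day 0 | days 7-10 | 21-18 |
| Week 2, day 14 (not scheduled) | days 21-24 | 7-4 |
| Week 4, day 28 | days 35-38 | 0 |

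The Baseline row can stop dosing, but an abnormality first seen there precedes treatment. After an Early Termination draw the drug has already been taken back, so that row also leaves nothing to stop.

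**3. Latest useful first draw.** For confirmation by day 28, the first abnormal draw must fall no later than 28 − 10 = day 18 (10-day retest) or 28 − 7 = day 21 (7-day retest). No scheduled draw after Baseline meets this.

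**4. What the rule can still do on days 35-38.** Week 6 is day 42, so confirmation comes 42 − 38 = 4 to 42 − 35 = 7 days before the last visit. The header's action (ending treatment) is no longer available. The item's own action (leaving the study) is, and taken literally it forgoes the Week 6 visit.

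**5. CPK.** The blood tests named at any visit are CBC with differential, CMP and CRP. CPK is named in the limit but in no visit list and no Table 1 row. AST, ALT and bilirubin are not named there either, so all the chemistry limits rely on what the CMP contains, and the protocol does not list its contents. On the assumption that the CMP covers AST, ALT and bilirubin but not CPK, scheduled tests never evaluate the CPK limit. If this site's panel includes CPK, the point reduces to saying so.

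**6. What a Week 2 draw would gain.** Planned applications: 28 × 2 = 56. If dosing continues until the retest, which the protocol does not settle, stopping on day 21 spares 7 × 2 = 14 (25%) and stopping on day 24 spares 4 × 2 = 8 (14%), in an affected patient.

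**The case against.** The strongest reply is that scheduled tests are not the only route. Safety Evaluation lets the investigator evaluate more often when clinically indicated. Safety Monitoring has an investigator review every laboratory result and calls for immediate discontinuation if safety is compromised. A confirmed related adverse event of grade 3 or higher is a separate ground for withdrawal. All of this stands, so it would be wrong to infer that a laboratory abnormality can never stop dosing. But each route needs a prompt, and a silent change gives none before Week 4.

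A second reply is that exposure is low. The cream goes on the face only, at no more than 60 g per week, for 4 weeks. Potential Risks cites plasma levels well below systemic activity, and strong CYP3A4 inhibitors and clinically significant hepatic or hematologic disease are excluded. This stands, and whether such a trial needs a mid-treatment blood test is a clinical judgement.

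Third, leaving the study includes leaving treatment, so the item is broader than its header rather than contradictory. That is fair. The practical difficulty is that, after Week 4, the broader action costs follow-up and stops no drug.

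A reader might also infer that the hemoglobin-drop limit, which requires a fall "from baseline on two consecutive blood draws with associated symptoms", cannot be evaluated because a completer has one scheduled draw after Baseline. The documents do not support that: the mandated retest supplies the second draw. The limit shares the timing problem and adds nothing to it.

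Finally, the Study Design Overview mentions blood collection in a sentence covering Weeks 2, 4 and 6 together. That wording is general, and neither the Week 2 nor the Week 6 list carries it through.

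**Conclusion.** The point holds as a minor mismatch between a safety rule and its schedule. From scheduled tests, an abnormality that arises on treatment is first seen when drug is being retrieved; after Week 4 it is confirmed 7-10 days past the end of dosing. This part rests only on the visit lists, Table 1 and nominal visit days. The CPK part is conditional on the CMP not including CPK. It should not be read as an established fact that CPK goes unmeasured.

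A reader might also infer a material hazard to patients. The documents do not support that: they give no rate of laboratory abnormality with topical use, so no number of affected patients can be derived, and the expected impact is small. The primary analysis is unaffected.

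**What to change.** 1. Add CPK to the Baseline and Week 4 chemistry already drawn, or delete the CPK limit. If CPK is added, summarize it descriptively so that it does not join the laboratory analytes tested under the Bonferroni adjustment in Analysis of Secondary Endpoints. Cost: at most 25 × 2 = 50 assays and no extra draw, or nothing if the limit is deleted. If the CMP already includes CPK, one sentence saying so is enough.

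2. Reword the laboratory item so that a confirmed abnormality stops study drug if it is still being applied, and the patient stays in safety follow-up through Week 6 or until resolution. Cost: wording only.

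3. Optional, for the sponsor's clinical judgement: either add CBC with differential and CMP at the existing Week 2 visit, or state that the limits act as triggers for follow-up after treatment. The first choice costs at most 25 draws (75 CPK assays in all if CPK is included at Week 2) and fits the Study Design Overview. It should come with a statement on whether drug is held until the retest, since that determines how much dosing is spared.

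None of these adds a scheduled visit.
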